2. Secondary (comparison of each listed parameter between the prospective treatment groups in addition to comparison of each treatment group with historic controls):
 - a. Growth (rate of change)

- i. Weight, length, and head circumference at enrollment, on a weekly basis while receiving study lipid, and 2-3 weeks post-study lipid completion.
- ii. Weight, length, and head circumference at 36 weeks corrected gestational age and time of discharge.
- b. Essential fatty acid profile differences and development of deficiency
- c. Average total caloric intake for all patients on weekly basis
 - i. Average lipid dose delivered on weekly basis
- d. Feeding tolerance/ percentage of total calories from enteral feeds
 - i. Time to achievement of enteral autonomy (full enteral feedings)
 - ii. Percentage of enteral calories at end of study
 - iii. Percentage of patients in each group with enteral autonomy
- e. Transaminase, alkaline phosphatase, GGT levels at enrollment, every 4 week time point, and end of study
- f. Triglyceride concentration at baseline, weekly, and end of study
- g. Rates of other diagnoses in each study group
 - i. Retinopathy of prematurity as diagnosed by Ophthalmologic examination
 - ii. Chronic lung disease as defined by need for oxygen at time of discharge or 36 weeks corrected gestational age (if at least 28 days of age), whichever comes first.
- h. Rates of adverse and serious adverse events in each group
- i. Length of stay
- j. Two year neurodevelopmental differences using ASQ-3 screening

Study Population

Inclusion criteria

Infants admitted to the Riley Hospital Neonatal Intensive Care Unit (NICU), regardless of postmenstrual or corrected gestational age, with anticipated need for parenteral nutrition for four or more weeks PLUS one or more of the additional inclusion criteria listed below will be eligible for inclusion within the study and for randomization. Inclusion criteria include:

- Anatomic intestinal defect: Neonate with intestinal atresia, omphalocele, gastroschisis or volvulus with or without intestinal resection and need for parenteral nutrition pre or post-operatively.
- Ischemic/perforation intestinal injury: Neonates with spontaneous intestinal perforation or necrotizing enterocolitis requiring surgical intervention with need for parenteral nutrition post-operatively.

Exclusion criteria at time of study enrollment

- Infant with current weight less than 750 grams

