A group of 24 patients previously treated in the Riley NICU from the years 2016 – 2017 will be used as a historic control cohort. Historic patients will be eligible for enrollment in the study if they have one of the above listed diagnoses, received post-operative parenteral nutrition, and were treated with soy-based lipid at standard dosing (2-3 g/kg/day). Historic patients will be ineligible to participate if any of the above listed exclusion criteria are true at the time of their abdominal surgery. Historic patients will be matched to prospective patients when able. This matching will first utilize in order: 1. days of parenteral lipid therapy, 2. diagnosis, 3. birth gestational age, and 4. birth weight when selecting for inclusion.

Study Procedures

1. Smoflipid® (20% lipid emulsion) treatment group
 - a. Advancement:
 - i. Smoflipid will be started at 1 g/kg/d on day 1 of parenteral nutrition after enrollment and advanced by 1 g/kg/d each subsequent day to a goal maximum of 3 g/kg/d
 - b. Maintenance and weaning [8]:
 - i. The Table below will be used as a guide for weaning Smoflipid as enteral nutrition is initiated and advanced.
 - ii. Patients will continue to be monitored by a clinical dietitian and pharmacist as per standard of care. Pending their recommendations, along with the clinical state of the child, the actual dose of Smoflipid needed may vary by individual patient.
 - c. Other parenteral nutrition components
 - i. Amino acid will be provided to meet estimated protein requirements only and will not be increased as a form of caloric intake.
 1. Term infant approximate goal of 3 g/kg/day and preterm infant approximate goal of 3.5 – 4 g/kg/day.
 - ii. Glucose infusion will be utilized and advanced per standard protocol to provide remainder of estimated non-protein caloric need of each individual patient.
 1. Maximum glucose infusion rate (GIR) while enrolled in study of 16 mg/kg/min. If further caloric intake is required, Smoflipid will be increased to a maximum of 3 g/kg/d.

Table 1: Smoflipid dosage recommendations for weaning as enteral feeds advanced

% calories from PN	Volume enteral feeds (ml/kg/d)	Enteral calories (kcal/kg/d)	Lipid (g/kg/d)
80-100%	\leq 20-40	\leq 30	3
60-80%	40-60	30-40	3
50-60%	60-80	40-50	2.5
40-50%	80-100	50-60	2
30-40%	100-110	60-70	1.5
20-30%	120	70-90	1
<20%	>120	>90	0

2. Intralipid® (20% lipid emulsion) reduction treatment group
 - a. Advancement:
 - i. Intralipid:

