- ii) In adequate patient recruitment. We anticipate recruiting an average of 4 patients per study month. If there is a significant lag and will be unable to obtain our full number of patients within a reasonable time, this will be reason to terminate the study early.
- b) Principle investigators will consider study cessation if SAEs occur within a specific treatment arm out of proportion to what would be expected from typical disease course.

Statistical Considerations

Our goal is to recruit 25 patients into each group. Given this is a pilot study, the minimum number needed per arm would be 12 patients as per published statistician recommendations [21]. The reasoning for using a pilot study include determining the feasibility of performing a larger scale study. Performing a pilot study prior to the large-scale study will give us information on patient recruitment and retention, along with design flaws that may be remedied prior to future studies.

All data will be summarized by group at each time point; summaries will include frequencies and proportions for categorical variables and mean, standard deviation, and range for continuous variables. Distributions of continuous variables will be examined. Parenteral nutrition characteristics will be recorded and tabulated. Tabulated categorical outcomes will include: proportions of subjects with cholestasis or IFALD, essential fatty acid deficiency, enteral autonomy at end of study, retinopathy of prematurity, chronic lung disease, and adverse events. Tabulated continuous measurements will include: growth rates, essential fatty acid profile, total caloric intake, percentage of calories from enteral intake, time to enteral autonomy, lipid dose delivered, bilirubin level, liver enzymes, gamma-glutamyl transferase (GGT), triglycerides, and length of stay. Fisher's Exact Tests will be used to compare between groups for categorical variables. Time to enteral autonomy will be evaluated using Kaplan-Meier survival curves and a log-rank test. Mixed models will be used to compare between groups and compare within groups over time for continuous variables measured throughout the study. Length of stay will be compared using a Wilcoxon Rank Sum test. A 5% significance level will be used for all tests mentioned.

Privacy/Confidentiality Issues

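### The 24 historic controls behind both primary comparisons are chosen from completed charts, with no reproducible selection rule and no masking of the outcome

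*Combined protocol and SAP*

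**What the plan says.** The Specific Aim and the primary objective compare the rate of cholestasis in each prospective arm with a historic cohort given soy-based lipid at standard dosing. Under Historic Controls (the section that follows Enrollment/Randomization) the cohort is fixed as "A group of 24 patients previously treated in the Riley NICU" in 2016–2017. No reason is given for the number.

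To be eligible, a control needs a listed diagnosis, parenteral nutrition (PN) after surgery, and standard-dose soy lipid. The exclusions are dated to surgery: "Historic patients will be ineligible to participate if any of the above listed exclusion criteria are true at the time of their abdominal surgery". The prospective infants must also be admitted "with anticipated need for parenteral nutrition for four or more weeks PLUS one or more of the additional inclusion criteria"; the expected-duration part of that is not repeated for controls.

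On selection, the plan says "Historic patients will be matched to prospective patients when able", in this order: "1. days of parenteral lipid therapy, 2. diagnosis, 3. birth gestational age, and 4. birth weight when selecting for inclusion". The later Historic Controls section under Study Procedures says that the data come from chart review. Neither section states the size of the eligible pool, who selects, which of the up to 50 prospective infants the 24 are matched to, or whether the selector is kept from the bilirubin results.

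**The concern.** One cohort is the comparator for both primary contrasts, so an error in its cholestasis rate enters both in the same direction. A retrospective comparator is credible when its membership is settled by a rule that does not depend on the outcome. Here two careful people following the text could assemble different sets of 24.

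The matching order makes this worse. Its first variable is known only once the course is over, so selection as written requires opening the part of the record that covers the same weeks as the bilirubin results. The variable is also post-baseline, and the course of the liver disease may itself influence how long lipid is given. Nothing in the plan separates the act of selecting from knowledge of the outcome.

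At stake is the control rate, which decides the primary result and which the sponsor hopes to use in choosing a direction for a larger study.

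**Working it through.** **Is there a derivation of 24?** No. The plan gives no control rate, effect size or power target, so there is no formula to reproduce. The number equals the prospective minimum (2 × 12 = 24), but the plan does not link the two.

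**Which parts of a selection rule are present?**

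| Element | In the plan? |
|---|---|
| Eligibility criteria | Yes, without the expected PN duration of four or more weeks |
| Calendar window | Yes, 2016–2017 |
| Order of matching variables | Yes; the first is post-baseline |
| Ratio, caliper, tie-break | No |
| What to do when no match exists | No |
| Consecutive or random order | No |
| Count of eligible infants | No |
| Masking of outcome at selection | No |

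**How far can a few charts move the result?** Inputs: 25 per arm (Enrollment/Randomization), 24 controls (Historic Controls), Fisher's exact test at 5% (Statistical Considerations). The test is taken as two-sided, which the plan does not state. The event counts are illustrative. With 5/25 events in an arm:

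| Controls with cholestasis | Fisher p |
|---|---|
| 10/24 | 0.128 |
| 11/24 | 0.072 |
| 12/24 | 0.038 |

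Exchanging two charts crosses the 5% level. With 4/25 in the arm, one exchange does so: p = 0.062 against 10/24 and 0.032 against 11/24. With 6/25, three are needed from the same start: 0.232 against 10/24 and 0.042 against 13/24.

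**Precision, as a secondary matter.** The pool size is unknown. The only flow figure is a forecast for the trial, under Study Stopping Criteria: "We anticipate recruiting an average of 4 patients per study month". Applied to 24 months it gives 4 × 24 = 96; half that flow gives 2 × 24 = 48. I use 48 to 96 as an assumed range, before the lipid-dose criterion is applied. The 95% half-width for arm minus control, with an assumed 40% cholestasis in both groups, is 1.96 × √[0.24 × (1/n + 1/m)], where n is the arm size, m the number of controls, and 0.24 = 0.40 × 0.60.

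| Controls (m) | n = 25 | n = 12 |
|---|---|---|
| 24 | 27.4 points | 33.9 points |
| 48 | 23.7 points | 31.0 points |
| 96 | 21.6 points | 29.4 points |

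For example, n = 25 and m = 24: 0.24 × (0.0400 + 0.0417) = 0.0196; √0.0196 = 0.140; × 1.96 = 27.4 points. The arm's own size limits the gain: at n = 25 it is 27.4 − 23.7 = 3.7 to 27.4 − 21.6 = 5.8 points, and at n = 12 it is 33.9 − 31.0 = 2.9 to 33.9 − 29.4 = 4.5 points.

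**The case against.** **The plan does constrain selection.** It gives eligibility criteria, exclusions dated to surgery, and four ordered matching variables. The qualifier on feasibility attaches to the matching; it does not say that controls are picked at will. This stands, and it narrows the room for choice. It does not make the choice reproducible, because nothing says how close a match must be or which of two similar charts is taken.

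**The pool may be small.** A reader might infer from the forecast of 4 a month that 24 are taken from about 96, a quarter of those available. The documents do not support that. The forecast concerns prospective recruitment, and the plan itself provides for slower enrolment. Control eligibility is narrower in requiring post-operative PN and standard-dose soy lipid, and wider in omitting the four-week expectation. The true count could fall below 48 or above 96. If it is close to 24, the precision argument disappears and there is little discretion left to remove.

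**Nobody is shown to be steering.** A reader might also infer that the unblinded study team selects with the outcomes in view. The plan does not name the selector, and its statement on blinding concerns the randomised treatments. What the documents support is that no masking at selection is specified.

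**Matching on lipid days has a purpose.** It is the plan's only device for aligning length of exposure. Taking all eligible infants without replacing it could admit controls with short PN and make the contrast less comparable. This stands, and the change below has to deal with it.

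**This is a pilot with no power target.** That is a fair reason to rank precision second. It does not answer the selection problem, since the plan tests at 5% and means to learn from the result.

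**Conclusion.** The point holds as an open door to selection bias in the primary comparator. The plan specifies neither a reproducible rule for choosing the 24 controls nor any masking of bilirubin when they are chosen, and its leading matching variable sends the selector into the completed course. With illustrative counts near 5/25 against 10/24, two charts decide whether p is above or below 5%. This shows how sensitive the result is; it is not evidence that any bias has occurred or an estimate of its size.

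The gain in precision from more controls is real but moderate: about 4 to 6 points of half-width at 25 per arm and 3 to 4.5 at 12. It rests on an assumed pool of 48 to 96 and an assumed 40% rate in both groups, neither of which the documents give. The change should be made, and it can be made without altering the enrolment or treatment of any prospective infant.

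**What to change.** In Historic Controls:

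1. Replace the selected 24 with every eligible infant from 2016–2017. If chart time does not allow this, take consecutive infants backwards from December 2017 to a number set in advance.
2. Apply to controls the same criterion on expected PN duration as to prospective infants, judged from information available around surgery. Keep the existing criteria: diagnosis, post-operative PN, standard-dose soy lipid, and the exclusions at surgery.
3. Lock the list before any later bilirubin result is opened, preferably by someone without access to those results, and report how many infants were eligible.
4. Drop the discretionary matching, including matching on lipid days. Handle diagnosis, birth gestational age and birth weight by stratification or adjustment in the analysis, kept simple because the numbers are small.

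Cost: on the assumed pool, 48 − 24 = 24 to 96 − 24 = 72 further charts. PN and lipid records must be opened for every candidate, because eligibility depends on them, so the work goes beyond the primary-endpoint fields. The cohort may also be less closely matched on individual characteristics than a hand-matched one. If the eligible pool turns out to be near 24, the extra work is small and the selection rule is still made explicit.

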- AST or ALT greater than 5 times the upper limit of normal within 2 weeks of enrollment

- Direct bilirubin greater than 2 mg/dL on any consecutive measurement 5-7 days apart within 2 weeks of enrollment
- Severe coagulopathy with elevated INR greater than 2.0 or clinically significant bleeding as determined by the primary and research teams
- Culture confirmed sepsis with positive blood, urine, or CSF culture within 2 weeks (14 days) of enrollment
- Renal failure requiring dialysis
- Cyanotic heart disease requiring prostaglandin therapy
- Hypertriglyceridemia (greater than 250mg/dL) at time of enrollment

Enrollment/Randomization

A maximum total of 50 prospective patients, 25 per arm, will be enrolled in the study. Patients will be eligible for enrollment if they meet the above listed enrollment criteria. Once patients are determined to meet enrollment criteria, the parents of the patient will be approached and informed consent will be obtained. Please see separate informed consent document for full consent details.

Stratified randomization will be used to divide patients into each treatment group. Patients will be initially stratified based on the diagnosis of necrotizing enterocolitis or spontaneous intestinal perforation (ischemic/perforation group) or anatomic intestinal abnormality. Once stratified based on diagnosis, patients in each stratum will then be randomized to receive either Smoflipid or Intralipid reduction as described below. Group randomization will be based on premade concealed envelopes.

This study will not be blinded as the caloric dose of the lipid strategies will vary and potentially influence other TPN dosing. Both IV lipids will be given as a solution separate from the remaining TPN. This separate IV lipid will be given as two 12 hour infusions over a 24 hour period.

In the event of slower than anticipated patient enrollment, a minimum of 24 patients (12 per treatment group) will be enrolled in order to obtain needed feasibility data.

Historic Controls

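### Historic controls enter under different rules from the randomised infants: no four-week anticipated-PN criterion, exclusions applied at surgery, and no common start or end for counting cholestasis

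*Combined protocol and SAP*

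**What the plan says.** The Specific Aim and the primary objective compare the number of infants with cholestasis on each lipid strategy with historic controls. Cholestasis needs two direct bilirubin values above 2 mg/dL, 5–7 days apart. No start or end of counting is given.

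**Entry.** Under Inclusion criteria, randomised infants are those "with anticipated need for parenteral nutrition for four or more weeks PLUS one or more of the additional inclusion criteria". For anatomic defects the wording is "with or without intestinal resection and need for parenteral nutrition pre or post-operatively". Under Historic Controls, "Historic patients will be eligible for enrollment in the study if they have one of the above listed diagnoses, received post-operative parenteral nutrition" and had soy lipid at 2–3 g/kg/day.

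**Screening date.** The randomised infants' list is headed "Exclusion criteria at time of study enrollment" and includes "Direct bilirubin greater than 2 mg/dL on any consecutive measurement 5-7 days apart within 2 weeks of enrollment". For controls: "Historic patients will be ineligible to participate if any of the above listed exclusion criteria are true at the time of their abdominal surgery".

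**Observation.** Laboratory monitoring gives randomised infants bilirubin at least weekly. Study Duration caps study lipid at 84 days, and one further set of labs follows at 2–3 weeks or at discharge. For controls, the chart-review section covers the whole Riley admission, with laboratory values taken where the record has them.

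**Matching.** "Historic patients will be matched to prospective patients when able", in the order "1. days of parenteral lipid therapy, 2. diagnosis, 3. birth gestational age, and 4. birth weight when selecting for inclusion".

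**The concern.** A historic comparison is interpretable only if controls are infants who could have been enrolled, with follow-up starting and stopping at the same point. Here the three defining elements (who enters, when they are screened, how long cases are counted) all differ, and all three bear on the primary outcome.

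The screening date matters most directly, because the bilirubin exclusion has the same threshold and spacing as the endpoint. An infant who turns cholestatic after surgery but before enrolment is barred from the randomised arms. The same infant in 2016–2017 passes screening at surgery and can be counted as a control case.

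The plan then tests categorical outcomes with an unadjusted Fisher's exact test at 5%, so nothing in the analysis corrects for these differences. The stated purpose is to choose a future direction for two lipid strategies, and a distorted control rate would feed straight into that choice.

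**Working it through.** **1. The rules side by side**

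| Element | Randomised infants | Historic controls |
|---|---|---|
| Expected PN | Four weeks or more | No duration required |
| Timing of PN | Pre- or post-operative (anatomic group) | Post-operative |
| Exclusions applied at | Enrolment | Abdominal surgery |
| Bilirubin | At least weekly on study lipid | As found in the record |
| Observation | At most 84 days of study lipid, then one set of labs | Whole Riley admission |

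**2. Direction of each difference**

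- *Entry.* Short-course infants admitted as controls would tend to lower the control rate.
- *Screening date.* If enrolment follows surgery, controls gain cases that are excluded prospectively. If an infant is enrolled before surgery on pre-operative PN, the offset reverses: cholestasis between enrolment and surgery counts prospectively but excludes a control. The phrase about two weeks of enrolment also does not say whether it looks back only.
- *Window.* Longer admission raises the control rate. Bilirubin pairs never drawn lower it.

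**3. Illustration**

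The documents give no cholestasis rate, so there is no plan figure to reproduce. From the documents: 25 (minimum 12) per arm, 24 controls, 5% level. Assumed: 12-week risk p = 0.40 at constant hazard, no lipid effect, two-sided test. Rejection probabilities are exact, by enumerating all pairs of binomial outcomes.

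- Entry: control rate = p − d(p − r), where d is the excess share of short-course infants and r their risk. 0.40 − 0.05 × (0.40 − 0.10) = 0.385; 0.40 − 0.20 × (0.40 − 0.05) = 0.330.
- Time zero and window together: control rate over T weeks = 1 − 0.6^(T/12). T = 10 gives 0.347, T = 12 gives 0.400, T = 14 gives 0.449, T = 16 gives 0.494.
- Missed control cases, share m: 0.40 × (1 − m). m = 0.10 gives 0.360; m = 0.30 gives 0.280.

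| Departure (one at a time) | Control rate | Shift (points) | Fisher rejection, 25 vs 24 | 12 vs 24 |
|---|---|---|---|---|
| None | 40.0% | 0 | 4.0% | 2.9% |
| Entry, d = 5 points, r = 10% | 38.5% | −1.5 | 4.0% | 2.9% |
| Entry, d = 20 points, r = 5% | 33.0% | −7.0 | 5.9% | 3.9% |
| 10 weeks observed | 34.7% | −5.3 | 5.0% | 3.4% |
| 14 weeks observed | 44.9% | +4.9 | 5.6% | 3.7% |
| 16 weeks observed | 49.4% | +9.4 | about 9% | 5.5% |
| 10% of cases missed | 36.0% | −4.0 | 4.5% | 3.1% |
| 30% of cases missed | 28.0% | −12.0 | 10.4% | 6.7% |

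The screening date has no row of its own. Under constant hazard, counting an extra one or two weeks between surgery and enrolment gives 0.425 or 0.449, which are simply the 13- and 14-week risks. If controls were counted for 12 weeks from surgery, the shift would be zero. The rows should not be summed.

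**4. Could the results reveal the bias?** With 10/25 against 10/24 cases, the Newcombe 95% interval for the difference is about −27 to +24 points. Every shift above lies inside it.

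**The case against.** The strongest reply has four parts.

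- *Matching deals with it.* Lipid days come first in the matching order, so controls with short courses may be passed over, and part of the window difference may shrink too. That much stands. But matching is only where possible, with no ratio or tolerance, and it creates no common time zero or window. Lipid days also accrue after baseline and depend partly on the outcome, because study lipid stops at direct bilirubin of 3 mg/dL or more on two draws.
- *The same information is collected for controls.* The protocol says so, and it says the listed labs other than INR could be considered standard of care. Control bilirubin may therefore be adequate, and a reader should not infer that it is poor. Collecting the same variables still does not set a shared window, and no rule checks completeness.
- *The effects are modest and may offset.* This largely stands. Most of the illustrated departures leave false rejection close to its nominal level, and all rates are assumed. Nothing in the plan makes the effects cancel, however.
- *It is a pilot justified by feasibility, with no power claim.* True, but this comparison is its primary objective and is tested at 5%.

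A reader might infer that the design favours the study lipids, since cases arising between surgery and enrolment count only among controls. The documents do not support that. The entry difference and missed cases pull the other way, and the offset reverses for infants enrolled pre-operatively.

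**Conclusion.** The concern holds as a design fault that should be fixed. Eligibility, screening date and ascertainment window differ between the randomised infants and the historic controls on the primary comparison, and matching does not align them. Those differences can be read directly from the text.

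The size and net direction of the bias cannot be determined. The figures above rest on an assumed 40% risk, constant hazard and assumed ranges for case mix, observation time and missed cases. They show only that shifts of several points either way are plausible and would go unnoticed at these sample sizes. They do not show that the primary comparison will be badly wrong. Aligning the rules removes avoidable differences but not the general limits of a historic comparison.

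**What to change.** 1. Add the four-week anticipated-PN criterion to control eligibility. Judge it from notes up to the index date, without sight of later bilirubin or actual PN duration.
2. Before charts are selected, fix one rule for a control index date equivalent to enrolment, with a version for infants who would have qualified on pre-operative PN. Apply all exclusions and two-week periods at that date, and state whether those periods look back only. Report surgery-to-enrolment intervals for the randomised infants so that any remaining offset is visible.
3. In all three groups, count cholestasis from the index date (enrolment for randomised infants) to the earliest of day 84, lipid or PN off for more than 7 days, and discharge or transfer from Riley. Add surgery date and lipid start and stop dates to the control chart abstraction. It now lists PN dates but only maximum and weekly average lipid dose, and no surgery date.
4. Report bilirubin draw frequency by group and the number of controls with no evaluable pair of draws. Include a sensitivity analysis counting those controls first as non-cases and then as cases.
5. Match on characteristics known at the index date (diagnosis, birth gestational age, birth weight) rather than on total lipid days.
6. Report the historic comparison with confidence intervals.

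The cost is protocol wording and somewhat more chart review. Eligible controls may be fewer, and the protocol does not give the size of the 2016–2017 pool. Judging anticipated PN from old notes is partly subjective.
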